Upon consent into the study, the patients will receive a Fitbit. For both arms of the study, Hugo will be used as a data collection platform as it aggregates data from multiple real-world data sources, thereby enabling the assessment of patient-reported outcomes, clinical outcomes, and healthcare utilization metrics. All participants will receive materials on sleep hygiene and healthy sleep tips. These sleep hygiene recommendations and healthy sleeping tips include behavioral information regarding getting a good night's sleep (e.g. setting a regular bed-time, getting out of bed if remaining awake, exercising regularly, not smoking). A full list of these tips can be found in **Appendix 1**. Patients will also receive a informational wallet card with study contact information (Appendix 8). Participants randomized to PEAR-003b will receive access to the therapeutic for 9

weeks a in addition to the sleep hygiene material. Post assessment data will be collected post intervention via diaries and questionnaires as outlined in the “Follow-up” section.

Because the Hugo platform obtains patient data through patient portals, all patients who connect will need a YNHH MyChart account. If the patient does not yet have a MyChart account, the RA will assist the patient in creating one. The RA will then assist the patient in linking their YNHH electronic health records to the Hugo platform as well as other health systems where they have received care by showing the study participant how to enter their patient portal credentials, provided that these health systems are connected to the Hugo platform.

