Upon enrollment and following syncing of the Hugo and Fitbit devices (with assistance from the RA), patients in both study arms will complete a baseline assessment that will include questionnaires as well as 10 days of sleep diaries within a 14-day window. Questionnaires will relate to insomnia severity (ISI), depression (PHQ-8), daytime sleepiness (ESS), stress (PSS-10), health-related quality of life (SF-12) and anxiety (GAD-7). Please see **Appendix 2** for original paper versions of questionnaires. These PROMs will also be administered using the Hugo platform at 9-, 21-, 35-, and 61- weeks post-randomization. The RA will also ask patients to obtain credentials, if necessary, and connect portals to health systems where they receive care that are connected to Hugo but were unable to connect at enrollment. Patients will also receive a follow-up email from the RA that includes user guides for the Fitbit Inspire 2 (**see Appendix 3**). After the 14-day window, the patients will be randomized. Patients randomized to PEAR-003b will be contacted by the RA and will be guided through installing and initiating the CBT-I app.

The RA will collect the following data at enrollment:

- Number of people asked for study participation and number enrolled.
- Number of study participants who required assistance setting up YNHH portal.
- Number who had YNHH portal who could not be enrolled (e.g. because they had forgotten password, no space on mobile device, technical glitch, etc.).

If a patient refuses to participate, then we will note the number of people who refused. If the patient is agreeable, we will then administer a short questionnaire to understand their rationale for not participating in the study, to understand potential reasons for non-participation. We will also ask these people who chose not to participate about basic demographics, if they are willing to answer (age, sex, race/ethnicity, major co-morbidities, insurance status). Please see **Appendix 4** for questionnaire.

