  - Patients are randomized by RA
  - Patients randomized to the PDT arm will be contacted by the RA and instructed on how to download and sign-up for Pear-003b.
- **Randomization through 9-week post-randomization**
  - Intervention Arm: Complete the Pear-003b PDT
  - Control Arm: Standard of Care
- **9-weeks post-randomization [~3 hours total]**

- Complete follow-up surveys: ISI; PHQ-8; GAD-7; ESS; PSS-10; SF-12
- Begin sleep diaries
- **21-weeks post-randomization [~3 hours total]**
  - Complete follow-up surveys: ISI; PHQ-8; GAD-7; ESS; PSS-10; SF-12
  - Begin sleep diaries
- **35-weeks post-randomization [~3 hours total]**
  - Complete follow-up surveys: ISI; PHQ-8; GAD-7; ESS; PSS-10; SF-12
  - Begin sleep diaries
- **61-weeks post-randomization [~3 hours total]**
  - Complete follow-up surveys: ISI; PHQ-8; GAD-7; ESS; PSS-10; SF-12
  - Begin final sleep diaries
  - Complete close-out questionnaire

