### 6.3.7 Removal of subjects

Discontinuation of the study intervention will be limited to voluntary patient discontinuation. Patient data will be monitored to watch for gaps in the device data of greater than 7 consecutive days, missed survey responses, as well as portal connection issues. Should an issue be noted, study staff will try to contact patients.

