## 6.4 Statistical Method

### 6.4.1 Statistical Design

All analyses of results from this RCT will be conducted as intent-to-treat (ITT) to avoid the effects of crossover and dropout. We will report baseline descriptive statistics for the overall study, by site, and for both the control and treatment arms of the study. These will include patient age, sex, race, ethnicity and all co-morbidities, medical history and clinical characteristics. Baseline data will be compared using Pearson Chi Squared tests or Fisher exact test for dichotomous and/or categorical variables and student's t-tests for continuous variables. If variables are deemed as non-parametric, we will use a median test such as a Mann–Whitney *U*-test, where appropriate.

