### 6.4.2 Sample Size Considerations

Analyses solving for minimum detectable effect sizes with 80% power were conducted with PASS software for only the primary outcomes (PASS 15). Because the models assume that each outcome is normally distributed, the outcome effects represent the average amount each outcome is expected to change with incremental shift in any explanatory variable. We will recruit a total of 100 participants and will randomly assign them to treatment and control arms based on a 50% probability of assignment. We also assume a 10% rate of drop-out between baseline and the end of follow-up, resulting in an effective sample size of N=80. Assuming a two-sided alpha threshold of 0.05, for the main outcome (change in ISI from baseline to 9-weeks post-randomization), and a power of 90% this sample size will allow us to detect an effect size of  $d=0.52$  which is  $\frac{1}{2}$  to  $\frac{1}{3}$  of what we have seen previously. Because this effect size is smaller than the levels demonstrated in randomized controlled trials, we are adequately powered to detect changes of interest in the main ISI outcome. We further note that this calculation is conservative because analysis may optionally draw from outcome values recorded at baseline and each follow-up time.

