### 6.4.3 Planned Analysis

#### 6.4.3.1 Primary Analyses

For the primary endpoint analysis, we will use a  $t$  test to compare the ISI scores for the intervention (PDT + Fitbit) and control group (Fitbit only) at baseline (as this score is a continuous variable). We will then use a 2 (group)  $\times$  2 (time) repeated measures analysis of variance (RM ANOVAs) to compare pre to post changes from baseline to 9-weeks across groups. Paired sample  $t$  tests by group will be used to examine time effects within each condition (if the overall interaction effect is significant). At weeks 21, 35, and 61 post randomization we will also perform the same analysis, but this will be as an exploratory secondary endpoint. If a patient drops out, we will carry forward the most recent patient-reported outcome measure response. As this is an RCT, we expect that confounding will be minimal. If patients are missing outcome data, we will use the last observation carried forward for the patient-reported outcome. Missing covariates will be set to missing.

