#### **6.4.5 Handling of Missing Data**

If patients are missing outcome data, we will use the last observation carried forward for the patient-reported outcome. Missing covariates will be set to missing.

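### Carrying the last value forward gives a patient with no week-9 ISI a change of exactly zero in the primary analysis, and no other missing-data rule or sensitivity analysis is planned

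*Combined protocol and SAP*

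**What the plan says.** Section 5.2.1 defines the primary outcome as the change in ISI from baseline to week 9. Section 6.4.3.1 analyses it by a 2 (group) × 2 (time) repeated measures ANOVA, so only the baseline and week-9 values enter. The same section gives the rule for drop-outs: "If a patient drops out, we will carry forward the most recent patient-reported outcome measure response". Section 6.4.5 makes it general: "If patients are missing outcome data, we will use the last observation carried forward for the patient-reported outcome". The only other missing-data statement concerns covariates. No sensitivity analysis is described.

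The ISI is completed at the enrollment visit (section 6.3.5). After that, section 6.3.4 says: "These PROMs will also be administered using the Hugo platform at 9-, 21-, 35-, and 61- weeks post-randomization". The schedule in section 6.3.1 shows no survey between enrollment and week 9.

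Section 6.4.1 sets the population: "All analyses of results from this RCT will be conducted as intent-to-treat (ITT) to avoid the effects of crossover and dropout". On expected loss, section 6.4.2 says: "We also assume a 10% rate of drop-out between baseline and the end of follow-up, resulting in an effective sample size of N=80". Section 6.3.7 foresees gaps other than withdrawal, since staff will watch for "missed survey responses, as well as portal connection issues".

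For the other patient-reported outcomes, section 6.4.3.2 names a repeated measures mixed model with an unstructured covariance matrix and Satterthwaite degrees of freedom. Section 6.4.5 does not exempt them from last observation carried forward (LOCF).

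**The concern.** LOCF is usually pictured as carrying a recent on-treatment value forward. Here the only earlier ISI was taken before randomization, so the rule asserts that a patient with no week-9 ISI did not change at all, and the analysis treats that as data. It applies to early drop-outs and equally to patients who skip week 9 and answer at week 21, because LOCF looks only backward. Patients who leave after giving a week-9 ISI are unaffected at the primary endpoint.

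Zero change is not a neutral guess in either arm. PDT patients are expected to improve. Controls may improve too: section 6.3.4 says "All participants will receive materials on sleep hygiene and healthy sleep tips", and section 6.3.5 lists "Control Arm: Standard of Care". The trial is unblinded (section 6.1.3), so loss could differ by arm. LOCF therefore cannot be defended as reliably conservative, and nothing in the plan would show how far the result depends on it.

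**Working it through.** **Inputs from the documents.** 100 patients randomized 1:1, taken as 50 per arm; two-sided alpha 0.05; drop-out of 10% by the end of follow-up. That 10% would leave 100 × 0.90 = 90 patients, whereas the N=80 stated beside it implies 20%. No loss at week 9 and no loss by arm is given.

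**Assumptions.** SD of change 5 ISI points; missingness unrelated to outcome; mean improvements and loss by arm as shown. The loss patterns 16%/4%, 4%/16% and 12%/8% (PDT/control) keep overall loss at the planned 10%.

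**Step 1: bias.** In a 2 × 2 repeated measures ANOVA the group-by-time interaction is the two-sample t test on change. Let p be the share of an arm without a week-9 ISI, and m the true mean improvement of those patients. LOCF replaces m by 0, so under any missingness mechanism

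bias = pC·mC − pT·mT.

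It vanishes only if the two products balance, for example if no missing patient truly changed.

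**Step 2: a real effect.** Take improvements of 6.5 (PDT) and 3 (control), a true difference of 3.5. The expected LOCF estimate is (1 − pT) × 6.5 − (1 − pC) × 3. Power is from 40,000 simulated trials per case, using the same t test on LOCF change and on observed change. Ranges cover fixed and binomial numbers missing.

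| Loss PDT/control | LOCF estimate (true 3.5) | Power, LOCF | Power, observed change |
|---|---|---|---|
| 10%/10% | 5.85 − 2.70 = 3.15 | 0.88–0.89 | 0.91 |
| 12%/8% | 5.72 − 2.76 = 2.96 | 0.83–0.85 | 0.91 |
| 16%/4% | 5.46 − 2.88 = 2.58 | 0.72–0.73 | 0.90–0.91 |
| 20%/10% | 5.20 − 2.70 = 2.50 | 0.70–0.71 | 0.89 |

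At 4%/16% the LOCF estimate is 6.24 − 2.52 = 3.72, above the truth.

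**Step 3: no true effect.** Both arms improve equally. Two improvements are shown because the bias is proportional to this assumption.

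| Loss PDT/control | Spurious difference, 4 points | Type I error, 4 points | Type I error, 3 points |
|---|---|---|---|
| 10%/10% | 0 | 4–5% | about 5% |
| 12%/8% | 0.08 × 4 − 0.12 × 4 = −0.16 | about 5% | about 5% |
| 20%/10% | 0.10 × 4 − 0.20 × 4 = −0.40 | 6–7% | about 6% |
| 16%/4% | 0.04 × 4 − 0.16 × 4 = −0.48 | 7–8% | 6–7% |

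These errors mostly run against PDT. At 4%/16% the sign reverses: false claims of PDT benefit occur in about 7% of trials (4 points) or 5–6% (3 points), instead of 2.5%.

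**Step 4: the alternative.** A five-visit simulation (1,500 runs; half of the missing patients drop out and half skip week 9 only) was analysed by a mixed model with baseline as a response. For a true 3.5 it gave 3.52 at 10%/10% and 3.53 at 20%/10%, against 3.17 and 2.54 under LOCF. Its null rejection rate was 5.1–6.5% over three loss patterns, with simulation error of about 0.6 percentage points and approximate degrees of freedom. This supports less bias; it is too coarse to show better error control.

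**Step 5: engagement correlations.** Section 6.4.3.2 correlates change in ISI and PHQ-8 with PDT use. A missing end-of-treatment value also becomes zero change there. If the arm improves and the missing patients are the less engaged, that can create a correlation. With a true correlation of 0, n = 50, 10% missing, a 1.6 SD improvement and moderate dependence, the mean Pearson correlation is −0.13, with 15% false positives. With a 0.52 SD improvement it is −0.05 with 5%.

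**The case against.** The size depends on imbalance that the documents do not predict. With equal 10% loss the cost is two or three points of power and no inflation. At 12%/8% type I error stays near 5%, though power still falls to about 0.84. The large figures need a fourfold imbalance or 15% loss overall. The plan also works to prevent gaps: an email reminder after 24 hours, a call after a further 48 hours (section 6.3.5), contact after missed surveys (section 6.3.7), and payment on response (section 7.1). No week-9 window is stated, so a late reply might still count. Finally, a missing-at-random analysis can be further from the truth than LOCF. Suppose 10% are missing in each arm, observed improvements are 6.5 and 3, and only the missing PDT patients were truly unchanged. The truth is then 0.9 × 6.5 − 3 = 2.85, LOCF gives 3.15, and missing-at-random gives 3.5.

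All of this is fair, and it limits the severity. It does not rescue the rule. Reminders and payment reduce the number missing without changing how those patients are scored. The remark in section 6.4.2 that analysis may optionally use all follow-up values is not a missing-data method, and the primary model uses two time points. That the right assumption is uncertain is a reason to test it, and the plan has no such test.

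**Conclusion.** The point holds. From the rule and the visit schedule alone, a patient with no week-9 ISI enters the primary ITT analysis as zero change. The resulting bias can go either way. It is small if loss is low and equal between arms: a 10% shrinkage of the effect at 10% loss. It becomes material if loss is clearly unequal: power of about 0.72 instead of 0.90 at 16%/4%, or false claims of PDT benefit in about 5–7% of trials instead of 2.5% at 4%/16%. These figures rest on assumed loss by arm, improvements of 3 to 6.5 points, an SD of change of 5, and missingness unrelated to outcome. This is not fatal, but it should be fixed before the data are analysed.

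**What to change.** - Delete LOCF from sections 6.4.3.1 and 6.4.5.
- Analyse ISI at all visits with the unstructured mixed model and Satterthwaite degrees of freedom already named in section 6.4.3.2, with the week-9 arm contrast as primary. Enter baseline as a response with a common mean across arms. Patients with only a baseline ISI then stay in the ITT model, and later visits inform a skipped week 9. ANCOVA with multiple imputation is a defensible alternative.
- State that the other patient-reported outcomes are likewise analysed without LOCF.
- Report the number without a week-9 ISI by arm.
- Add one missing-not-at-random sensitivity analysis, by delta-adjusted or reference-based multiple imputation. Let the delta range reach zero change for missing PDT patients, so that it includes what LOCF now assumes for that arm.
- For the engagement correlations, use observed change, report the number missing by engagement level, and note that the complete cases may themselves be selected.

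The cost is SAP wording and some programming, with no new data. The price is reliance on missing-at-random in the primary analysis, which the sensitivity analysis is there to probe.

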#### 6.4.3.2 Secondary Objectives Analyses

For the secondary endpoint analysis regarding the patient reported outcomes, we will calculate the change in the PHQ-8, ESS, SF-12, PSS-10^22 and the GAD-7 scores at baseline and at 9-weeks, 21-weeks, 35-weeks and 61-weeks post randomization (as these are continuous variables) and perform a comparison between patients randomized to the intervention (PDT + Fitbit) and patients randomized to the control (Fitbit only). Based on our prior work using SHUTi, we will examine the change in scores between groups using a mixed model repeated measures ANOVA with an unstructured matrix, and estimated degrees of freedom (df) with Satterthwaite's correction. We will present df alongside F-test statistics and t statistics.

For the secondary clinical/healthcare utilization outcomes we will compare the PDT to the control at all follow-up time points. These outcomes will be defined as: (a) number of outpatient visits per patient with primary care physicians, (b) number of outpatient visits per patient with specialty care, (c) number of medication refills for sleep per patient, and (d) number of medication refills for psychotropic medications per patient. These comparisons will be examined using *t* tests at each time point (as these will be continuous variables).

For the sleep outcomes, we will calculate the change in each sleep outcome from baseline to 9-weeks, 21-weeks, 35-weeks, and 61-weeks post randomization comparing PDT to the control based on sleep diaries. These outcomes will be defined as: (a) sleep efficiency; (2) sleep onset latency [SOL], (3) number of awakenings, (4) sleep quality, and (5) total sleep time (minutes) (6) waking after sleep onset [WASO], (7) time in bed. We will examine the change in scores between groups using a mixed model repeated measures ANOVA. Paired-sample *t* tests will be used to examine time effects within each condition if the overall interaction effect is significant.

For the secondary health utilities outcome, we will calculate the change in health utilities scores from baseline to 9-weeks, 21-weeks, 35-weeks and 61-weeks post randomization (as these are continuous variables) and perform a comparison between patients randomized to the intervention (PDT + Fitbit) and patients randomized to the control (Fitbit only). Health utilities scores are derived from the SF-6D algorithm as applied to the SF-12 data.

For the secondary engagement outcome, we will examine the relationship between engagement with PDT and clinical outcomes in the PDT arm at all follow up time points. Correlations between engagement and clinical outcomes will be evaluated using both Pearson's correlation coefficient and Spearman's rank correlation as follows. Change from baseline (Follow up – baseline) will be calculated for ISI, sleep diary-derived metrics of SOL and WASO, and PHQ-8, at both the end of treatment and the end of all follow-ups. These will be correlated with core completion rates, sleep diary completion rate, and the number of times the PDT is opened. In addition, clinical outcomes among those who complete all six cores of treatment will also be examined.

Lastly, the exploratory physical and sleep activity outcomes (measured using Fitbit) will again be compared from baseline to 9-weeks, 21-weeks, 35-weeks, and 61-weeks comparing PDT to control. These outcomes will be defined as: (a) number of steps per day; (b) sleep [total sleep time in minutes], and (c) self-reported metrics such as weight, height, and BMI). We will examine the change in scores between groups using a mixed model repeated measures ANOVA. Paired-sample *t* tests will be used to examine time effects within each condition if the overall interaction effect is significant.

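### If last observation carried forward feeds the engagement correlations, a PDT patient with no week-9 survey has an ISI and PHQ-8 change of exactly 0, which can create part of an apparent engagement benefit that no planned output would reveal

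*Combined protocol and SAP*

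**What the plan says.** Section 6.4.3.2 defines change as follow-up minus baseline for ISI, PHQ-8 and diary SOL and WASO, at the end of treatment and the end of follow-up, in the PDT arm. It continues: "These will be correlated with core completion rates, sleep diary completion rate, and the number of times the PDT is opened". Both Pearson and Spearman coefficients are planned. It adds: "In addition, clinical outcomes among those who complete all six cores of treatment will also be examined". It states no missing-data rule for these analyses.

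Section 6.4.5 reads: "If patients are missing outcome data, we will use the last observation carried forward for the patient-reported outcome". The same sentence stands in 6.4.3.1, which also says: "If a patient drops out, we will carry forward the most recent patient-reported outcome measure response". Section 6.4.1 makes every analysis intent-to-treat.

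On timing, section 6.3.4 places the scales at baseline and then says: "These PROMs will also be administered using the Hugo platform at 9-, 21-, 35-, and 61- weeks post-randomization". The visit list in 6.3.5 agrees: the first entry after randomization that reads "Complete follow-up surveys: ISI; PHQ-8; GAD-7; ESS; PSS-10; SF-12" is week 9.

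On loss, section 6.4.2 says: "We also assume a 10% rate of drop-out between baseline and the end of follow-up, resulting in an effective sample size of N=80". Section 6.3.7 provides for monitoring of "missed survey responses, as well as portal connection issues. Should an issue be noted, study staff will try to contact patients".

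**The concern.** With no ISI or PHQ-8 between baseline and week 9, the value carried forward for a week-9 non-responder is the baseline score, so the change is 0 by construction. Improvement is negative on this scale. If non-responders used the PDT less and the others improved, the forced zeros sit at the low-engagement end and pull r below 0, which reads as more engagement, more benefit.

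The relation between engagement and outcome is secondary objective 3 (section 4.3). Section 3.2 lists it among the things the study will teach and says the data will inform reimbursement discussions. As written, an imputation rule could supply part of the coefficient, and no planned output would show how much. The look at six-core completers would be largely free of forced zeros if non-responders rarely finish six cores, but it does not measure the contribution of LOCF to r.

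**Working it through.** **Plan's own figures.** The plan gives no expected value, precision or power for the engagement correlations. Its loss figures disagree: 10% of 100 leaves 90, whereas N=80 implies 20%. It does not say how much loss falls before week 9. Spread evenly over four follow-ups, 10% gives 2.5% per visit and 20% gives 5%. Placing all the loss before week 9 gives 10% and 20%.

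**Inputs.** The PDT arm has about 50 patients (100 randomized 1:1; sections 5.3.1 and 6.1.3). The rest are assumptions:
- p: share with no week-9 survey.
- k: mean improvement of responders divided by the SD of change. For ISI, k = 1.0 to 1.6. Section 6.4.2 calls d=0.52 one half to one third of earlier results, so about 1.04 to 1.56. That is only a loose anchor for a within-arm change. For PHQ-8, k = 0.2 to 0.5.
- d: responder minus non-responder mean engagement, in responder SDs; v: ratio of engagement variances (non-responders to responders). With responders spread evenly over 0 to 6 cores (mean 3, variance 4) and non-responders over 0 to 2 (mean 1, variance 2/3), d = (3-1)/2 = 1 and v = (2/3)/4 = 1/6.

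**Step 1. No true association, non-responders set to 0.**

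r = -k·p(1-p)·d / sqrt{[(1-p) + p(1-p)k²]·[(1-p) + p·v + p(1-p)d²]}

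For p=0.10 and k=1.0: numerator 0.09; change variance 0.90+0.09 = 0.99; engagement variance 0.90+0.0167+0.09 = 1.0067; r = -0.09/sqrt(0.99×1.0067) = -0.090.

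| Early loss p | ISI, k=1.0 | ISI, k=1.6 | PHQ-8, k=0.2 | PHQ-8, k=0.5 |
|---|---|---|---|---|
| 2.5% | -0.024 | -0.038 | | |
| 5% | -0.047 | -0.073 | | |
| 10% | -0.090 | -0.135 | -0.019 | -0.047 |
| 20% | -0.164 | -0.234 | -0.036 | -0.088 |

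Simulation with n=50 gave ISI values of -0.090/-0.137 at 10% and -0.160/-0.236 at 20%; Spearman was similar or slightly larger. A smaller gap (d=0.5, v=1) gives -0.045/-0.067 at 10% and -0.080/-0.114 at 20%. An extreme split, in which every responder completes at least three cores (d=3.13, v=0.53), gives -0.209/-0.313 and -0.325/-0.463.

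**Step 2. When the shift vanishes or reverses.** With d=0 or k=0 the numerator is 0, so r stays at 0. If non-responders are more engaged by 1 SD, simulation at 20% loss (k=1.04) gives +0.16.

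**Step 3. Non-responders' true change is 0.** Take k=1.3, d=1, v=1/6 and no association among responders. LOCF then puts non-responders at the right mean and removes only their spread, so the full-data change variance is 1 + p(1-p)k².
- p=0.10: full data -0.117/sqrt(1.1521×1.0067) = -0.109; LOCF -0.117/sqrt(1.0521×1.0067) = -0.114.
- p=0.20: full data -0.208/sqrt(1.2704×0.9933) = -0.185; LOCF -0.208/sqrt(1.0704×0.9933) = -0.202.

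Simulation agrees (full data about -0.11/-0.18, LOCF -0.115/-0.20), while observed pairs and multiple imputation give about 0 and miss the association. If non-responders truly worsened (by 0.5 SD, at 20% loss and k=1.04), LOCF understates it: -0.16 against -0.20.

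**Step 4. Scale.** The 95% half-width around r=0 is tanh(1.96/sqrt(n-3)). At n=50 this is tanh(0.286) = 0.28.

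**The case against.** The strongest counter-argument is that the shift is measured against a truth in which barely engaged non-responders improved as much as everyone else. Step 3 shows that if they gained little, LOCF is close to the full-data answer and the alternatives erase a real association. This stands, and it rules out calling LOCF wrong here or requiring multiple imputation in its place. Another run points the same way: with missingness depending on both engagement and a worse outcome, and a true r of 0, LOCF gave -0.05/-0.10 at 10%/20% loss, observed pairs +0.06/+0.10 and multiple imputation +0.06/+0.10. The choice is among untestable assumptions.

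It is also fair that 6.4.3.2 never says LOCF feeds these correlations, and that 6.4.5 repeats a sentence from the primary analysis. A reader might infer that the plan prescribes LOCF here; it does not do so outright. But 6.4.5 is a stand-alone section with no stated limit, and no other rule exists. If LOCF was not intended, the correlations have no rule at all.

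The size may be negligible. At the stated 10% spread evenly, the shift is 0.02 to 0.04 against a half-width of 0.28. Reminders, phone calls, monitoring and payment per survey (sections 6.3.5, 6.3.7 and 7.1) should limit missed surveys. That lowers the priority but leaves the rule unchanged for surveys still missed.

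A reader might also infer that every drop-out receives a 0. Patients lost after week 9 carry a real post-baseline value, and the week-61 change is 0 only if no follow-up survey is ever returned.

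**Conclusion.** The point holds in a conditional form. Following the written text, a PDT patient with no week-9 survey has an ISI and PHQ-8 change of exactly 0 in the week-9 correlation. This pushes r towards an engagement benefit only if such patients are less engaged, the PDT arm improves on average (the trial's hypothesis), and the non-responders' true change is not near 0. The documents establish none of the three, so they do not support a reading that the coefficient will be biased in the product's favour.

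Under the assumed 1 SD engagement gap and an ISI improvement of 1.0 to 1.6 SD, the shift is negligible at 2.5% early loss, 0.09 to 0.14 at 10% and 0.16 to 0.24 at 20%; for PHQ-8 it is under 0.1 throughout. Whether LOCF covers diary SOL and WASO is not stated, so they are left out.

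Priority is minor: engagement is not randomized, the result is descriptive and no test is planned. It is still worth settling, because the planned outputs cannot separate an association in the data from one produced by the zeros.

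**What to change.** In 6.4.3.2 and 6.4.5:
1. State that the ISI and PHQ-8 engagement correlations will not rest on carried-forward values alone. Compute the planned Pearson and Spearman coefficients on observed pairs, with the LOCF version beside them as a sensitivity analysis.
2. Tabulate the number with missing week-9 and week-61 ISI and PHQ-8 by engagement level, for example cores completed.
3. Interpret an engagement association as robust only if it appears both with and without carried-forward values.

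Multiple imputation, with the engagement measures and all observed scores in the model, is an optional further sensitivity analysis.

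Cost: a short clarification, one table and a second set of coefficients; no new data. Intervals widen slightly: the half-width around r=0 goes from 0.28 at n=50 to tanh(1.96/sqrt(42)) = 0.29 at n=45 and tanh(1.96/sqrt(37)) = 0.31 at n=40. Observed pairs can be biased if missingness depends on outcome, and attenuated by a narrower engagement range. In an extreme simulated case (assumed 1.3 ISI points per core, responders with at least three cores), full-data r of -0.36/-0.42 at 10%/20% loss fell to -0.27/-0.28. The report should state both limits beside the coefficients.
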